4.2 Number of Centers

Approximately 40 centers are expected to participate in this study.

4.3 Number of Patients

Blinded Phase:

A total of 210 patients will be targeted to be enrolled. The 210 patients will be randomly allocated to one of four treatment groups (GWP42003-P 25 mg/kg/day, GWP42003-P 50 mg/kg/day, placebo 25 mg/kg/day dose volume equivalent, or placebo 50 mg/kg/day dose volume equivalent) at a 2:2:1:1 ratio. The placebo groups will be pooled for the analyses of efficacy. If it is assumed that patients in the placebo group will experience a mean reduction in seizure frequency of 15% (from baseline), patients receiving GWP42003-P will experience at least a 50% reduction in seizures and a common standard deviation of 60%, then this sample size of 70 patients per group will be sufficient to detect a difference in response distributions with 90% power. This test is based on a two-sided non-parametric Mann-Whitney-Wilcoxon test for continuous response data with a 5% significance level.

Open-label Extension:

All patients who wish to continue on IMP following the blinded phase.

The sample size calculation is explained fully in [Section 13.1](#).

Study Code: GWEP1521
 EudraCT Number: 2015-002154-12
 Protocol V8 23Apr19

5 INVESTIGATIONAL MEDICINAL PRODUCT

Please refer to the separate Pharmacy Manual for more detailed information on the IMP.

5.1 GWP42003-P Solution

GWP42003-P solution is presented as a clear, colorless to yellow solution containing 100 mg/mL CBD dissolved in the excipients sesame oil and anhydrous ethanol (10% v/v) with added sweetener (sucralose) and strawberry flavoring (Table 5.1-1).

Material	Quantity
CBD	100 mg/mL
Anhydrous ethanol	79 mg/mL
Sucralose	0.5 mg/mL
Strawberry flavoring	0.2 mg/mL
Sesame oil	make up to 1 mL

5.2 Placebo Solution

Placebo solution is presented as a clear, colorless to yellow oily solution containing the excipients sesame oil and anhydrous ethanol (10% v/v) with added sweetener (sucralose) and strawberry flavoring (Table 5.2-1).

Material	Quantity
Anhydrous ethanol	79 mg/mL
Sucralose	0.5 mg/mL
Strawberry flavoring	0.2 mg/mL
Sesame oil	make up to 1 mL

5.3 Packaging, Storage and Drug Accountability

5.3.1 Packaging and Labeling

The IMP will be manufactured, packaged, labeled and/or distributed by G-Pharm or delegated contractors. The IMP will be presented in 100 mL amber glass bottles with child-resistant caps and packed in cartons. Sufficient IMP will be dispensed at each relevant visit considering the dose group and weight of each patient. A unique identification number will be used to identify each box and the IMP it contains. The unique identification number together with the packaging reference number (PRN) will permit full traceability of manufacture, pack and label activities conducted at or on behalf of G-Pharm and the IMP information held on the IVRS. G-Pharm will

Study Code: GWEP1521
EudraCT Number: 2015-002154-12
Protocol V8 23Apr19

ensure that all IMP provided is fully labeled and packaged. Label text will include the following information, as a minimum:

- Sponsor's name.
- Product identification (e.g., "GWP42003-P/placebo").
- Dose and/or Potency.
- Expiry date.
- Storage conditions.
- Instruction: "For clinical trial use only".
- Instruction: "Keep out of the sight and reach of children".

In addition, any local country requirements in accordance with local Drug Law or Regulatory Requirement will be included in the final label text.

The IMP labels for the blinded phase and the open-label phase of the trial will have different colors, so these can be easily distinguished by the patients. Directions of use, name, address and the telephone number of the investigator (or main contact for information about the product or the clinical trial) will be provided separately to the patient. Patients will be instructed to retain and carry this information with them at all times.

5.3.2 Storage

The IMP must be stored upright at room temperature (< 30°C) and must not be refrigerated or frozen. It must also be kept away from heat and direct sunlight.

The IMP must be stored in compliance with the local regulations for a controlled drug (if applicable to country). The sponsor must approve storage location and facilities. Temperature records of the clinical site storage location must be maintained (recording a minimum of Monday–Friday, excluding public holidays) from date of receipt of first shipment until end of study dispensing period at each center. These records must contain at least the minimum and maximum daily temperatures and should be made available to the appropriate GW personnel for review throughout the study. Temperature records taken during transit of IMP to center must be checked on receipt.

Should storage conditions deviate from these specified requirements, the GW study monitor must be contacted immediately to confirm if the IMP remains suitable for

Study Code: GWEP1521
EudraCT Number: 2015-002154-12
Protocol V8 23Apr19

use. IMP should be placed under quarantine until written confirmation is received that IMP is suitable for use.

IMP will be transported to country depots and clinical sites in compliance with Good Distribution Practice guidelines.

5.3.3 Supply and Return of Investigational Medicinal Product

All IMP will be shipped to approved depot facilities and clinical sites with a Product Release Certificate that includes a physical description of the product for confirmation of identity on receipt.

Once a center has been activated via the IVRS at study initiation, IMP will be shipped to the identified responsible person, such as the pharmacist, at the investigator's center, who will check the amount received (against the IVRS Shipment Request) and condition of the drug (i.e., integrity, physical appearance, temperature during transit). Details of IMP received will be recorded in the IMP accountability record (see [Section 5.3.4](#)). The center will acknowledge IMP receipt via the IVRS and will complete any receipt forms required. IMP will be dispensed and returned as detailed in [Section 8.4](#) with further IMP shipments to be initiated by IVRS. As directed, all supplies, including unused, partially used, or empty containers, will be returned to G-Pharm/depot or destroyed at a G-Pharm-approved site if agreed in writing by the study monitor.

5.3.4 Investigational Medicinal Product Accountability

The investigator has overall responsibility for the accountability of all used and unused IMP. A drug accountability record for the IMPs must be kept current and should contain:

- Study Code.
- PRN, Treatment number, date of receipt and quantity of IMP received.
- Patient's trial identification and/or Treatment number.
- Date and quantity of IMP dispensed.
- The initials of the dispensing/dosing party.
- Date and quantity of IMP returned to the investigator.
- IMP expiry dates.

Study Code: GWEP1521
EudraCT Number: 2015-002154-12
Protocol V8 23Apr19

IMP will be dispensed at Visits 3, 4, 5, 6, 7, 9 and 10 (patients not entering the OLE) during the blinded phase and Visits B1, B2, B3, B4, B5, B6, B7, B8 and B9. All patients will be asked to return all IMP (used and unused) to each subsequent visit. Any discrepancies will be discussed with the patient or their caregiver at the time of the visit and documented accordingly within the patient's source documents.

The investigator must inform GW promptly of all missing or unaccountable IMP.

A record of returned IMP must be completed and included in the shipment of used and unused IMP to GW or the relevant Drug Distribution Depot. At the end of the study, a record/statement of reconciliation must be completed and provided to GW.

These inventories must be made available for inspection by an authorized GW representative and local officials or regulatory agency inspectors.

Please refer to the separate Pharmacy Manual for more detailed information on the IMP.

Study Code: GWEP1521
EudraCT Number: 2015-002154-12
Protocol V8 23Apr19

6 PATIENT ELIGIBILITY

Investigators are responsible for confirming patient eligibility and will be required to maintain a log that includes limited information about all screened patients (initials, age, sex; as allowed per local regulations) and outcome of screening. After the screening visit, investigators will submit the patient's documented history of seizures directly to the Epilepsy Study Consortium (ESC) for verification of seizure types. The ESC may ask the investigator for additional information to assist in their decision. The decision will be made within 14 days of receipt of all required information and the ESC will provide written confirmation directly to the investigator.

6.1 Inclusion Criteria

For inclusion in the study, patients must fulfil ALL of the following criteria:

- 6.1.1 Patient is male or female aged between one and 65 years inclusive.
- 6.1.2 Patient and/or parent(s)/legal representative is willing and able to give informed consent/assent for participation in the study (see [Section 15.2](#)).
- 6.1.3 Patient and their caregiver are willing and able (in the investigator's opinion) to comply with all study requirements (including accurate diary and IVRS completion).
- 6.1.4 Well-documented clinical history of epilepsy, which is not completely controlled by their current AEDs.
- 6.1.5 Clinical diagnosis of TSC according to the criteria agreed by the 2012 International Tuberous Sclerosis Complex Consensus Conference¹⁹.
- 6.1.6 Taking one or more AEDs at a dose which has been stable for at least four weeks prior to screening.
- 6.1.7 All medications or interventions for epilepsy (including ketogenic diet and any neurostimulation devices for epilepsy) must have been stable for one month prior to screening and the patient is willing to maintain a stable regimen throughout the study.
- 6.1.8 Patient is willing to keep any factors expected to affect seizures stable (such as the level of alcohol consumption and smoking).
- 6.1.9 Patient and/or parent(s)/legal representative is willing to allow the responsible authorities to be notified of participation in the study, if mandated by local law.

Study Code: GWEP1521
EudraCT Number: 2015-002154-12
Protocol V8 23Apr19

6.1.10 Patient and/or parent(s)/legal representative is willing to allow his or her primary care practitioner and consultant (if they have one) to be notified of participation in the study, if mandated by local law.

At the end of the baseline period, patients must also meet the following criteria:

6.1.11 Experienced at least eight seizures during the first 28 days of the baseline period, with at least one seizure occurring in at least three of the four weeks (seizures include: focal motor seizures without impairment of consciousness or awareness; focal seizures with impairment of consciousness or awareness; focal seizures evolving to bilateral generalized convulsive seizures and generalized seizures ([tonic-clonic, tonic, clonic or atonic] that are countable).

6.1.12 Completed at least 90% of calls to IVRS during the first 28 days of the baseline period (a minimum of 25 completed calls).

6.2 Exclusion Criteria

The patient may not enter the study if ANY of the following apply:

- 6.2.1 Patient has a history of pseudo-seizures.
- 6.2.2 Patient has clinically significant unstable medical conditions other than epilepsy.
- 6.2.3 Patient has an illness in the four weeks prior to screening or randomization, other than epilepsy, which in the opinion of the investigator could affect seizure frequency.
- 6.2.4 Patient has undergone general anesthetic in the four weeks prior to screening or randomization.
- 6.2.5 Patient has undergone surgery for epilepsy in the six months prior to screening.
- 6.2.6 Patient is being considered for epilepsy surgery or any procedure involving general anesthesia during the blinded phase of the study.
- 6.2.7 Patient has been taking felbamate for less than one year prior to screening.
- 6.2.8 Patient is taking an oral mTOR inhibitor.
- 6.2.9 Patient has, in the investigator's opinion, clinically significantly abnormal laboratory values.

Study Code: GWEP1521
EudraCT Number: 2015-002154-12
Protocol V8 23Apr19

- 6.2.10 Patient has any known or suspected hypersensitivity to cannabinoids or any of the excipients of the IMP, such as sesame oil.
- 6.2.11 Any history of suicidal behavior or any suicidal ideation of type 4 or 5 on the C-SSRS in the last month or at screening.
- 6.2.12 Patient is currently using or has in the past used recreational or medicinal cannabis, or cannabinoid-based medications, within the three months prior to screening and is unwilling to abstain for the duration for the study.
- 6.2.13 Patient has tumor growth which, in the opinion of the investigator, could affect the primary endpoint.
- 6.2.14 In the opinion of the investigator the patient has clinically significant abnormalities in the ECG measured at screening or randomization or any concurrent cardiovascular conditions, which will interfere with the ability to read their ECGs.
- 6.2.15 Patient has significantly impaired hepatic function at the screening visit (Visit 1) or the randomization visit (Visit 3), defined as **any** of the following:
- i) Serum alanine aminotransferase (ALT) or aspartate aminotransferase (AST) $> 5 \times$ upper limit of normal (ULN).
 - ii) TBL* [serum total bilirubin] $\geq 2 \times$ ULN **or** international normalized ratio [INR] > 1.5 (*TBL $\geq 2 \times$ ULN exclusion will not apply for patients diagnosed with Gilbert's disease).
 - iii) Serum ALT or AST $\geq 3 \times$ ULN with the presence of fatigue, nausea, vomiting, right upper quadrant pain or tenderness, fever, rash, and/or eosinophilia ($> 5\%$).
- This criterion can only be confirmed once the laboratory results are available.*
- 6.2.16 Patient is female and of child bearing potential, or is male whose partner is of child bearing potential, unless willing to ensure that they or their partner use a highly effective method of birth control (e.g., hormonal contraceptives, intrauterine devices/hormone-releasing systems, bilateral tubal occlusion, vasectomized partner, sexual abstinence) during the study and for three months thereafter.
- 6.2.17 Female patient who is pregnant (positive pregnancy test), lactating or planning pregnancy during the course of the study and for three months thereafter.
- 6.2.18 Patient has received an IMP less than 12 weeks prior to the screening visit.

Study Code: GWEP1521
EudraCT Number: 2015-002154-12
Protocol V8 23Apr19

- 6.2.19 Patient has any other significant disease or disorder which, in the opinion of the investigator, may either put the patient at risk because of participation in the study, may influence the result of the study, or may affect the patient's ability to take part in the study.
- 6.2.20 Any abnormalities identified following a physical examination of the patient that, in the opinion of the investigator, would jeopardize the safety of the patient if they take part in the study.
- 6.2.21 Patient has donated blood during the past 12 weeks and is unwilling to abstain from donation of blood during the study.
- 6.2.22 Patient has been previously randomized into this study.
- 6.2.23 Patient has any known or suspected history of alcohol or substance abuse.
- 6.2.24 Patient has travel outside the country and/or state of residence planned during the trial, unless the patient has confirmation that the IMP is permitted in the destination country/state.

Study Code: GWEP1521
EudraCT Number: 2015-002154-12
Protocol V8 23Apr19

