	
defined as any of the following:
 
 – Serum alanine aminotransferase (ALT) or aspartate aminotransferase (AST) > 5 × upper limit of normal (ULN). – TBL* [serum total bilirubin] ≥ 2 × ULN or international normalized ratio [INR] > 1.5 (*TBL ≥ 2 × ULN exclusion will not apply for patients diagnosed with Gilbert’s disease). – Serum ALT or AST ≥ 3 × ULN with the presence of fatigue, nausea, vomiting, right upper quadrant pain or tenderness, fever, rash, and/or eosinophilia (> 5%). 
This criterion can only be confirmed once the laboratory results are available.
 
 • Patient is female and of childbearing potential, or is male whose partner is of child bearing potential, unless willing to ensure that they or their partner use a highly effective method of birth control (e.g., hormonal contraceptives, intrauterine devices/hormone-releasing systems, bilateral tubal occlusion, vasectomized partner, sexual abstinence) during the study and for three months thereafter. • Female patient who is pregnant (positive pregnancy test), lactating or planning pregnancy during the course of the study and for three months thereafter. • Patient has received an IMP less than 12 weeks prior to the screening visit. • Patient has any other significant disease or disorder which, in the opinion of the investigator, may either put the patient at risk because of participation in the study, may influence the result of the study, or may affect the patient’s ability to take part in the study. • Any abnormalities identified following a physical examination of the patient that, in the opinion of the investigator, would jeopardize the safety of the patient if they take part in the study. • Patient has donated blood during the past 12 weeks and is unwilling to abstain from donation of blood during the study. • Patient has been previously randomized into this study. • Patient has any known or suspected history of alcohol or substance abuse. • Patient has travel outside the country and/or state of residence planned during the trial, unless the patient has confirmation that the IMP is permitted in the destination country/state.

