
Criteria for Withdrawal
	
The patient must be withdrawn from the study if any of the following apply:
 
 • Administrative decision by the investigator, GW or regulatory authority. • Pregnancy. • Protocol deviation that is considered to potentially compromise the safety of the patient. • Withdrawal of patient consent/assent. • Withdrawal of parent(s)/legal representative consent. • ALT or AST > 3 × ULN with the appearance of fatigue, nausea, vomiting, right upper quadrant pain or tenderness, fever, rash, and/or eosinophilia (> 5%). • ALT or AST > 8 × ULN. • ALT or AST > 5 × ULN for more than two weeks. • ALT or AST > 3 × ULN and (TBL > 2 × ULN or INR > 1.5). • Lost to follow-up. 
Note: Prior to withdrawal for the transaminase elevations noted above, the investigator may choose to confirm the transaminase elevations by repeating the following laboratory tests within 24 to 48 hours: ALT, AST, TBL, INR, % eosinophils, gamma-glutamyl transferase and alkaline phosphatase. Should the above transaminase elevation criteria be confirmed, the patient must be withdrawn from the trial.
 
The patient may also be withdrawn from the study for any of the following:
 
 • Did not meet eligibility criteria. • Patient non-compliance. • AE (including clinically significant laboratory result) which, in the opinion of the investigator, would compromise the continued safe participation of the patient in the study. • Suicidal ideation or behavior of type 4 or 5 during the treatment period, as evaluated with the C-SSRS. • Any evidence of drug abuse or diversion. • General anesthesia (blinded phase only). • Addition of a new AED (blinded phase only).

Investigational Medicinal Product: Formulation,
	
GWP42003-P solution (100 mg/mL cannabidiol in sesame oil with anhydrous ethanol, sweetener [sucralose] and strawberry flavoring). Placebo solution (sesame oil) containing the excipients anhydrous

Study Code: GWEP1521
 EudraCT Number: 2015-002154-12
 Protocol V8 23Apr19

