7 PATIENT ENROLLMENT

Before patients may be entered into the study, GW requires a copy of the relevant center's Ethics Committee (EC) or Institutional Review Board (IRB) written approval of the protocol, informed consent/assent forms (ICF) and other patient information material. Patients will be considered enrolled in the study from the time of providing written informed consent/assent. All patients and/or parent(s)/legal representatives, where appropriate, must personally sign and date the consent and, if allowed per local regulations, assent forms prior to any procedures being performed (refer to [Section 9.2.1](#) and [Section 15.2](#)).

In the UK, enrollment of patients between the ages of 12 and 23 months will only commence once 15 patients over the age of 23 months have been dosed for a minimum of 4 weeks and no new safety issues have been observed.

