9.1.1.2 Visit 2 (Day -28, Baseline)

This visit will occur 7 days after Visit 1. A visit window of ± 7 days from the scheduled visit is permitted to ensure ESC confirmation of seizure classification, but it is preferred that the visit is performed on the scheduled visit day where possible.

Attendance of the patient is not required for this visit provided the primary caregiver is able to attend and that this caregiver (not the patient) will be responsible for seizure identification, IVRS use, and paper diary completion. However, it is preferred that the patient attend where possible.

The following observations will be made at Visit 2: review of concomitant medications (including AEDs), AEs and epilepsy-related hospitalizations.

Patients who satisfy all inclusion and none of the exclusion criteria specified in [Section 6](#) will begin the 28 (+3)-day baseline period. The investigator will review and train the patient or their caregiver to identify the patient's expected seizure types. Patients or their caregivers will be issued with IVRS details and will be instructed on how to use it to record daily seizure information. Patients or their caregivers will also be given a paper diary to record usage of IMP, rescue medication, concomitant AEDs and AEs and will be instructed on how to do so.

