9.1.1.3 Visit 3 (Day 1, Randomization)

This visit will occur 28 days after Visit 2. A visit window of +3 days from the scheduled visit date is permitted, but it is preferred that the visit is performed on the scheduled visit day where possible.

The following observations will be made at Visit 3: concomitant medications, (including AEDs), physical examination (including height and body weight), details of menstruation (for females), Tanner Staging (for patients aged 10–17 years [inclusive], or earlier if clinically indicated by onset of menarche or other signs of precocious puberty), ECG, vital signs, postural blood pressure, epilepsy-related hospitalizations, AEs and paper diary review. The ECG will be repeated four hours (± 30 minutes) after the first dose of IMP.

Clinical laboratory samples (blood and urine [where possible]), including pregnancy tests if appropriate (using both a serum sample and a urine dipstick), will be taken for hematology, biochemistry, urinalysis, and determination of serum IGF-1 levels (for

Study Code: GWEP1521
EudraCT Number: 2015-002154-12
Protocol V8 23Apr19

patients less than 18 years of age). Provided that the risk/benefit outcome is favorable in the investigator's opinion, prior to the first daily dose of IMP, a blood sample will be taken for analysis of plasma concentrations of concomitant AEDs. PK samples (patients > 20 kg in weight only) will be taken in accordance with [Section 9.2.9.1](#).

The investigator must assess the patient's daily number of seizures from the patient's IVRS data, record the patient's attendance at the visit, and confirm the outcome of the visit prior to randomization. Patients who have experienced at least eight seizures during the first 28 days of the baseline period, and who meet all of the other inclusion and none of the exclusion criteria specified in [Section 6](#), will be eligible to continue in the study.

Eligible patients will then be randomized to receive GWP42003-P 25 mg/kg/day, GWP42003-P 50 mg/kg/day, placebo 25 mg/kg/day dose volume equivalent, or placebo 50 mg/kg/day dose volume equivalent at a 2:2:1:1 ratio.

Following randomization at Visit 3, patients will remain at the clinic where the following baseline assessments will be performed prior to the administration of study medication: QOLCE/QOLIE-31-P, Wechsler Tests, CBCL/ABCL, SCQ and the Vineland-II. Suicidality will be assessed in accordance with [Section 9.2.12.8](#).

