10 WITHDRAWAL

In accordance with the Declaration of Helsinki⁵⁶, the ICH Tripartite Guideline for GCP Topic E6(R2)⁵², the U.S. FDA regulations relating to good clinical practice and clinical trials^{57,58,59}, the European Union (EU) Clinical Trials Directive⁶⁰, the EU Good Clinical Practice (GCP) Directive⁶¹ and/or other applicable regulations, a patient has the right to withdraw from the study at any time and for any reason without prejudice to his or her future medical care by the physician or at the institution.

The patient must be withdrawn from the study if any of the following apply:

- Administrative decision by the investigator, GW, or a Regulatory Authority.
- Pregnancy.
- Protocol deviation that is considered to compromise potentially the safety of the patient.
- Withdrawal of patient consent/assent.
- Withdrawal of parent(s)/legal representative consent.
- ALT or AST > 3 × ULN with the appearance of fatigue, nausea, vomiting, right upper quadrant pain or tenderness, fever, rash, and/or eosinophilia (> 5%).
- ALT or AST > 8 × ULN.
- ALT or AST > 5 × ULN for more than two weeks.
- ALT or AST > 3 × ULN **and** (TBL > 2 × ULN **or** INR > 1.5).
- Lost to follow-up.

Note: Prior to withdrawal for the transaminase elevations noted above, the investigator may choose to confirm the transaminase elevations by repeating the following laboratory tests within 24 to 48 hours: ALT, AST, TBL, INR, %eosinophils, gamma-glutamyl transferase and alkaline phosphatase. Should the above transaminase elevation criteria be confirmed, the patient must be withdrawn from the trial. In cases where the transaminase elevation withdrawal criteria are not met or confirmed, the dose of IMP or a concomitant AED with known hepatotoxicity should be reduced following discussion with the GW medical monitor.

Study Code: GWEP1521
EudraCT Number: 2015-002154-12
Protocol V8 23Apr19

Patients may also be withdrawn from the study for any of the following:

- Did not meet eligibility criteria.
- Patient non-compliance.
- AE (including clinically significant laboratory result) which, in the opinion of the investigator, would compromise the continued safe participation of the patient in the study.
- Suicidal ideation or behavior of type 4 or 5 during the treatment period, as evaluated with the C-SSRS.
- Any evidence of drug abuse or diversion.
- General anesthesia (blinded phase only).
- Addition of a new AED (blinded phase only).

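### The Gilbert's disease waiver in 6.2.15(ii) carries no transaminase condition, so a patient can pass the numeric hepatic exclusion with values that already require withdrawal under Section 10

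*Protocol*

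**What the plan says.** Entry. Protocol 6.2.15 defines significantly impaired hepatic function at Visit 1 or Visit 3 by any of three limbs:

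- (i) ALT or AST above 5 × ULN.
- (ii) TBL at or above 2 × ULN, or INR above 1.5. The synopsis and 6.2.15 both carry the waiver. In 6.2.15 the TBL ≥ 2 × "ULN exclusion will not apply for patients diagnosed with" Gilbert's disease; in the synopsis it reads "TBL ≥ 2 × ULN exclusion will not apply for patients diagnosed with" Gilbert's disease. Nothing in either place ties it to ALT or AST.
- (iii) ALT or AST at or above 3 × ULN, but only with a listed symptom or eosinophilia above 5%.

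A note adds: "This criterion can only be confirmed once the laboratory results are available".

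Withdrawal. The mandatory list in Section 10, repeated in the synopsis, includes "ALT or AST > 3 × ULN and (TBL > 2 × ULN or INR > 1.5". The investigator may repeat the tests within 24 to 48 hours first, but "Should the above transaminase elevation criteria be confirmed, the patient must be withdrawn from the trial". Section 12.8 lists the same four liver criteria for patients after randomization, requires a report within 24 hours, and treats raised transaminases with raised TBL as a potential drug-induced liver injury. Neither section mentions Gilbert's disease or a patient's own baseline as an exemption.

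**The concern.** Entry limits and stopping limits should fit together, so that nobody starts treatment in a state that the stopping rule already forbids. For patients without Gilbert's disease they do fit. The waiver removes the bilirubin limit at entry, while the combined transaminase and bilirubin stopping rule keeps it. A patient in the gap could be randomized and given a first dose, and then have to stop and be reported because of values present before any drug was taken. The first scheduled laboratory draw after dosing is at Visit 4 (Day 15). That is an avoidable exposure, possibly of a child, an avoidable early withdrawal, and a liver-injury report that says nothing about the drug.

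**Working it through.** The protocol gives no figure to reproduce; this is a check of threshold logic. Let A be the higher of ALT and AST, with A and TBL in multiples of ULN. A symptom below means any listed symptom or eosinophilia above 5%.

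Inputs:

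| Rule | Source | Condition |
|---|---|---|
| E1 | 6.2.15(i) | excluded if A > 5 |
| E2 | 6.2.15(ii) | excluded if TBL ≥ 2 (waived in Gilbert's) or INR > 1.5 |
| E3 | 6.2.15(iii) | excluded if A ≥ 3 with a symptom |
| W1 | Section 10 | withdrawn if A > 3 with a symptom |
| W2 | Section 10 | withdrawn if A > 8 |
| W3 | Section 10 | withdrawn if A > 5 for more than two weeks |
| W4 | Section 10 | withdrawn if A > 3 and (TBL > 2 or INR > 1.5) |

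**Without Gilbert's disease.** Passing E1 to E3 means A ≤ 5, TBL < 2, INR ≤ 1.5, and no symptom when A ≥ 3. W1 cannot be met because of E3. W2 and W3 cannot be met because A ≤ 5. W4 cannot be met because TBL < 2 and INR ≤ 1.5. There is no overlap.

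**With Gilbert's disease.** Only the limit TBL < 2 is lost. W1, W2, W3 and the INR arm of W4 still cannot be met. The TBL arm of W4 can. The overlap is exactly 3 < A ≤ 5, TBL > 2, INR ≤ 1.5 and no symptom.

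**Example.** Gilbert's disease, ALT 4, TBL 2.5, INR 1.0, no symptom. E1: 4 is not above 5. E2: TBL is waived and INR passes. E3: no symptom. The patient passes 6.2.15. W4: 4 > 3 and 2.5 > 2, so withdrawal is mandatory.

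**With the waiver limited to A ≤ 3.** A patient who passes with TBL > 2 must then have A ≤ 3, and W4 needs A > 3. The overlap is empty.

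**Enumeration as a cross-check.** Take A from 0.5 to 10 and TBL from 0.5 to 4 in steps of 0.1, INR 1.0, 1.5 or 2.0, symptom yes or no, and Gilbert's yes or no: 96 × 36 × 3 × 2 × 2 = 41,472 states. Of these, 7,242 pass 6.2.15. The overlap holds 20 values of A (3.1 to 5.0) × 20 of TBL (2.1 to 4.0) × 2 of INR = 800 states, all with Gilbert's disease. Limiting the waiver removes these 800 and a further 20 × 1 × 2 = 40 with TBL exactly 2.0, leaving 7,242 − 840 = 6,402 passing and none in overlap. The counts depend on the chosen ranges and step. They confirm the logic and say nothing about how many patients are affected.

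**Other routes out.** 6.2.9 (clinically significant laboratory abnormality) and 6.2.19 (other significant disease) turn on the investigator's opinion; they allow exclusion of this patient but set no numeric limit. Dose reduction for raised transaminases, in 8.1.2 and in the Section 10 note, is offered only when the withdrawal criteria are not met, so it does not provide a way to keep the patient on treatment.

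**The case against.** The strongest objection is that an investigator would exclude such a patient anyway. Section 12.8 itself treats this combination as a potential liver injury, so it is hard to call it not clinically significant under 6.2.9, and once that judgment is made exclusion is mandatory. This is a fair point and will often hold. It does not close the gap, because an explicit waiver can equally be read as permission to enroll.

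It can also be objected that the waiver is not unlimited: 6.2.15(i) still caps ALT and AST at 5 × ULN, limb (iii) excludes symptomatic patients from 3 × ULN, and INR above 1.5 still excludes. That is right, and it is why the gap is only the asymptomatic band above 3 and up to 5 × ULN.

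A reader might infer more: that the protocol gives opposite instructions from the day of consent. Section 7 states "Patients will be considered enrolled in the study from the time of providing written informed consent/assent", and Section 10 names no starting point, so a Visit 1 result could seem both to admit and to expel. The documents do not support making much of this. Meeting the entry criteria permits entry; it does not require that a patient be kept on drug. If Section 10 did apply from consent, the patient would leave before any dose, which does no harm. Section 10 also reads mainly as a set of on-treatment rules: its note speaks of reducing the study drug, and 12.8 applies the same criteria after randomization.

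A reader might also infer that safety results would be distorted. Baseline laboratory results go with every 12.8 report, 12.5 treats events starting before the first dose as not causally related, and 13.6.5.2 counts an event as treatment emergent only if it starts or worsens after the first dose.

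**Conclusion.** The gap is real and exactly bounded: diagnosed Gilbert's disease, ALT or AST above 3 and up to 5 × ULN, TBL above 2 × ULN, INR at or below 1.5, and no listed symptom or eosinophilia. The waiver is its only source. Followed as written, the numeric rules can lead to a patient being randomized and dosed who must then be withdrawn and reported on unchanged values. This rests on two assumptions: that the investigator does not exclude the patient under 6.2.9 or 6.2.19, and that the values persist on treatment and on any repeat test.

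The size is small. The protocol gives nothing from which to estimate how many screened patients fall in this region; few, if any, are likely. No patient is left unprotected, because the stricter rule governs once treatment starts, and the effect on the trial's conclusions is minor. It is a point to consider, worth making because the correction costs almost nothing.

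**What to change.** In 6.2.15(ii) and in the synopsis exclusion list, restrict the bilirubin waiver to diagnosed Gilbert's patients whose ALT and AST are both at or below 3 × ULN, at Visit 1 and again at Visit 3. Leave the thresholds in Section 10 and 12.8 unchanged. Exempting Gilbert's disease from the withdrawal rule instead would also remove the overlap, but would weaken a liver-safety rule.

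The recruitment cost is negligible. Besides the patients in the gap, the change excludes Gilbert's patients with ALT or AST above 3 × ULN whose TBL is exactly 2 × ULN, since exclusion uses at or above 2 and withdrawal uses above 2. It also excludes those whose transaminases would have fallen unaided.

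The change settles eligibility before dosing for values present at Visit 1. Visit 2 falls 7 ± 7 days after Visit 1, a window that "is permitted to ensure ESC confirmation of seizure classification", and Visit 3 falls 28 days after Visit 2 ("A visit window of +3 days from the scheduled visit date is permitted"). Visit 1 is therefore at least 0 + 28 = 28 days before the first dose. The change cannot prevent a first dose when values first cross the limits at Visit 3: under 9.1.1.3 that dose is given in clinic, under 9.2.9 the blood goes to a central laboratory, and the results may return later.
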